Patients will continue on their self-selected ad-lib diets. They will keep a food diary during the day before the urine collection and during the urine collection. They will then replicate the diet during each of the subsequent parts of the study, repeating the same diet on the day before and the day of the urine collection. We will collect the food diaries at the end of the study to ensure compliance and to keep a record of what the subjects were eating.

The urine will be collected with thymol and gentamicin as preservatives, and maintained at room temperature. The urine will be alkalinized at home with 10g of NaHCO3 as per the usual Litholink protocol for cystine measurement. Study participants will be asked to measure the volume of their urine and then mail an aliquot of their urine to a commercial laboratory, Litholink Corporation (Chicago, IL), for analysis. Another specimen will be mailed to Mayo Clinic for liquid chromatography mass spectrometry (LC/MS) testing.

The urine pH, sodium, urea, and creatinine will be measured by Litholink. Additionally, the cystine supersaturation, 24h urine cystine excretion and cystine capacity of each urine sample will be measured by the following method, the “solid phase” cystine assay. Measured amounts of cystine crystals will be incubated in the urine at 37°C for 48 hours with stirring. The residual solid phase will then be harvested by centrifugation at 3800 rpm for 20 minutes at room temperature and then dissolved in 25ml of high-pH buffer (0.1 M sodium carbonate; pH 9.9). The cystine concentration will be measured in both the supernatant liquid and the buffer to determine the change in solid phase, which is known as the cystine capacity.

The primary outcome of the study is to determine the effect of drug dosage on urinary cystine capacity. Thus, the mean cystine capacities in each part of the study (0 g/d, 500 mg/d, 1 g/d, and 2 g/d) will be compared. Urine urea, a surrogate of protein intake and urine sodium will be measured and compared to ensure diets are replicated correctly throughout the study period. Urine pH will be also measured to make sure similar amounts of alkali therapy are used in each part of the study.

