#### **4.3 Retention Strategies:**

Due to the short duration of the study (4 weeks), we do not anticipate the need for extensive retention strategies. Patients will be called periodically at least once a week during the 4-week study period to answer any questions they may have, and to ask about any adverse effects they may be experiencing.

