### 5.1 Study Oversight:

The Study Chair has primary oversight responsibility of this clinical trial. The NIH appointed Data Safety Monitoring Board (DSMB) has oversight responsibility of the Data Safety Monitoring Plan (DSMP) for this clinical trial. The DSMB will review accrual, patterns and frequencies of all adverse events, and protocol compliance every 6 months. The D/OSMB makes recommendations to the NIH regarding the continuation status of the protocol.

Each site's Principal Investigator and their research team (co-Investigators, research nurses, clinical trial coordinators, and data managers) are responsible for identifying adverse events. Either the Principal Investigator or one of the co-Investigators will call each subject weekly during the study period to remind them to change the dose of medication, and to assess for any potential adverse events. All subjects will undergo a blood test for complete blood count and urine test for urinalysis within one month of completing the study to monitor for any adverse effects from the changes in medication dosages. The results of the blood and urine tests will be reviewed by the Principal Investigator. All adverse events will be reported to the DSMB. Aggregate report- detailed by severity, attribution (expected or unexpected), and relationship to the study drug/study procedures – will be available from the DMCC for site review. The research

team will then evaluate whether the protocol or informed consent document requires revision based on the reports.

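### Food diaries are collected only after the fourth urine collection, so they can document a diet that was not replicated but cannot secure replication while it can still be corrected

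*Combined protocol and SAP*

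**What the plan says.** Section 4 (Study Design and Methods) lets subjects eat as they choose and then tries to hold that diet constant across the four 7-day parts. On recording it: "They will keep a food diary during the day before the urine collection and during the urine collection". On repeating it: "They will then replicate the diet during each of the subsequent parts of the study", specifically "repeating the same diet on the day before and the day of the urine collection". On checking it: "We will collect the food diaries at the end of the study to ensure compliance", and also as a record of intake.

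The same section has a second check. Urine urea, as a marker of protein intake, and urine sodium "will be measured and compared to ensure diets are replicated correctly throughout the study period".

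Two sections describe telephone contact. Section 4.3: "Patients will be called periodically at least once a week during the 4-week study period", for questions and adverse effects. Section 5.1: a weekly call "to remind them to change the dose of medication, and to assess for any potential adverse events". Section 5.3 repeats the weekly call for adverse effects. None of the three names diet.

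The mixed model in Section 6 contains dose and period effects. The later paragraph on statistical considerations adds a Friedman test and GLS regression without naming covariates.

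**The concern.** The aim given for collecting the diaries is to secure compliance, but the timing allows only a record of it. After a short screening visit everything happens at home, so a subject who misunderstands the instruction in the second period may carry the same mistake through the third and fourth before anyone sees a diary.

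The primary outcome is compared within subjects, from one 24-hour collection per dose. Any difference in diet between two of a subject's collections goes directly into that subject's dose difference. No diet covariate, repeat collection or sensitivity analysis is written that would deal with it afterwards. That leaves prevention as the main control, and the written plan has no step for prevention after the initial instruction.

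**Working it through.** **1. Timeline.** Inputs: four 7-day periods with a collection on day 7 of each (Section 4); Days 7, 14, 21 and 28 (Schedule of Events, Section 4.4); diet days are the day before and the day of collection (Section 4).

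- Diet days are therefore days 6 and 7 of each period: study days 6–7, 13–14, 20–21 and 27–28.
- The first pair sets the template. The other three pairs are replications.
- A diary collected at the end of the study is seen no earlier than Day 28.
- Replicated collections per subject that a diary review could still influence: 0 of 3.

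The text does not say outright that a new diary is kept in every period. I read it that way, because otherwise there would be nothing to compare with the template. The Schedule of Events as available lists dietary history at baseline and has no diary row. I give that little weight, since the table may be incomplete.

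**2. Other contacts.** The calls in Sections 4.3, 5.1 and 5.3 serve questions, dose changes and adverse effects. No call is timed relative to day 6.

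**3. The laboratory check.** Urea and sodium are measured in each collection, and aliquots are mailed after each one, so results might arrive during the study. Section 4 does not state when they are reviewed, what difference counts as non-replication, or what is then done. They reflect protein and sodium intake only.

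**4. Exposed collections.**

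- At 15 subjects (synopsis and sample size section): 15 × 4 = 60 collections, of which 15 × 3 = 45 (75%) rely on replication.
- If a problem is recognised after period 2: 15 × 2 = 30 are still ahead.
- At the 5–10 subjects given in Section 4: 15–30 of 20–40, the same 75%.

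**5. What added noise could do (illustration only).** The plan's figure of 9 participants at P=0.05 and 85% power cannot be reproduced, because no cystine capacity difference or SD is given. It can be solved backwards. For a two-sided paired t-test, power = 1 − F(t₀.₉₇₅,ₙ₋₁; df = n−1, noncentrality = d√n), with F the noncentral t distribution function. Setting n = 9 and power = 0.85 gives a standardized within-subject difference d = 1.142. The one-sided version gives 0.981, and the two-sided normal approximation gives (1.960 + 1.036)/3 = 0.999.

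Suppose unreplicated diet raises the variance of the within-subject difference by a fraction k. Then d becomes 1.142/√(1+k):

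| k (assumed) | d | Power, n = 9 | Power, n = 15 |
|---|---|---|---|
| 0 | 1.142 | 85.0% | 98.4% |
| 10% | 1.089 | 81.6% | 97.5% |
| 25% | 1.022 | 76.6% | 95.7% |
| 50% | 0.933 | 68.9% | 91.9% |
| 100% | 0.808 | 56.7% | 82.9% |

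Every k is an assumption. The table applies to the contrast used for sizing, which the plan describes as the largest change seen previously. Contrasts with smaller effects would have less margin.

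**The case against.** **Non-replication would not necessarily go unnoticed.** A reader might infer from the diary timing that a departure from the diet cannot be detected. The documents do not support that. Section 4 plans the urea and sodium comparison for exactly this purpose, and diaries read at the end can still show departures. Silence on when laboratory values are read does not prove that they come too late. This stands in full. What remains is that detection is partial, and that no in-study correction is written.

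**The subject needs the diary.** The first diary is the template for later periods, so leaving it with the subject has a function. This stands, and it is why a copy rather than the original should be sent.

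**The calls may already cover diet.** They are open to any question, and nothing excludes diet. That is true, but a question the subject does not think to ask is not a check, and nothing places a call before the diet days.

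**Randomization and the model limit the damage.** Section 4 randomizes the order of the parts for each subject, and Section 6 includes period effects. A shift between the first period and the rest that is common to subjects would be largely absorbed, and individual departures would become noise. This largely stands. It does not cover diet that changes because the subject knows the dose: no blinding is described, and such a change would follow dose in any order. Whether that would happen, and in which direction, is speculation. The synopsis also describes escalating doses in sequence; under a fixed order, diet drift would be confounded with dose.

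**The margin at 15 subjects is comfortable.** In the illustration, a 50% rise in variance still leaves about 92% power. This is fair for the contrast used for sizing if 15 subjects complete.

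**Conclusion.** The point holds as a matter of study conduct: collecting diaries at the end documents compliance and cannot ensure it, and the urea and sodium comparison is a partial check with no stated timing or consequence. Three quarters of the collections (45 of 60 at 15 subjects) depend on replication. This is a count of exposed collections, not an estimate of how many will fail.

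The likely effect is added within-subject noise in the primary comparison. Its size is unknown because the documents give neither a non-replication rate nor an effect of diet on cystine capacity.

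Two stronger readings are tempting and are not supported. One is that diet is the main nuisance factor for the outcome: Section 4 also monitors urine pH for alkali use, and the Background reports that cystine solubility measurements varied with pH. The other is that the off-drug comparison is biased: this is possible in an unblinded design, but nothing in the documents shows it.

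The conclusion assumes that a diary is kept in every period and that end of study means after the Day 28 collection. The change is worth making because it is cheap and comes early enough to act on, not because the trial's validity depends on it.

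**What to change.** Amend Section 4, with matching wording in Sections 4.3 and 5.1:

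- A diary is kept in every period. After the first collection the subject sends the study team a copy or photograph and keeps the original as the template. It goes to the study team, not with the urine, which is mailed to outside laboratories.
- In each later period, one of the planned weekly calls takes place by day 5 (study days 12, 19 and 26), before the diet days begin on day 6. The caller reads back the template and confirms the two replication days.
- After each later collection, a copy or photograph of that period's diary goes to the study team, so a misunderstanding can be corrected before the next collection.
- One added sentence should say when urea and sodium are reviewed and what follows if they differ.

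The cost is a few minutes of call time and some instruction wording. If the dose-change reminder has to stay at the change of period, one extra short call per period may be needed; the call frequency in Section 4.3 already permits it. No visit, test or staff is added. A reminder lowers the risk of non-replication but does not guarantee compliance, so the 45 collections should not be described as fully protected.

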#### **4.1 Inclusion Criteria:**

- Age between 18 and 80 years.
- Patients with a confirmed laboratory diagnosis of cystinuria who meet the following criteria: (1) stone analysis demonstrating cystine as a component, or (2) increased urinary cystine excretion (>250mg/24hrs in adults).
- A medical regimen that includes Tiopronin.
- Female patients who are willing to use a birth control method.
- Ability to reliably urinate in a collection vessel and measure urine volume.
- Ability to give informed consent.
- Documentation of a stable complete blood count (CBC) and urinalysis (UA) in the six month period prior to the date of enrollment.
- Enrollment in Rare Kidney Stone Consortium (RKSC) Protocol 6401 (Cystinuria Registry)

#### **4.1 Exclusion Criteria:**

- Pregnant patients.
- Patients with renal colic
- Patients who are scheduled to undergo a surgical procedure
- Inability to give informed consent

#### **4.2 Recruitment of Participants:**

Patients from [name] clinic and those who are enrolled in the RKSC protocol 6401 (Cystinuria Registry) will be contacted either by phone, mail, or email and recruited.

#### **4.3 Retention Strategies:**

Due to the short duration of the study (4 weeks), we do not anticipate the need for extensive retention strategies. Patients will be called periodically at least once a week during the 4-week study period to answer any questions they may have, and to ask about any adverse effects they may be experiencing.

#### 4.4 Schedule of Events:

	Baseline (Visit 1)	Day 7	Day 14	Day 21	Day 28	Day 29-60
Demographics (sex, date of birth)	x					
Baseline stone history (diagnosis date and method of diagnosis, review of current symptoms)	x					
Medication history (Current medications including Alkali therapy, and history of CBTDs including side effects, allergic reactions)	x					
Dietary history (fluid intake, low sodium, low protein, etc)	x					
24-hour urine collection		x	x	x	x	
Pregnancy Test	X					

## 5 Data and Safety Monitoring Plan

The study protocol will be reviewed and approved by the National Institutes of Diabetes and Digestive and Kidney Diseases (NIDDK) before submission to NYU Langone Health IRB for approval. Participant enrollment may only begin with IRB approved consent forms. This is an interventional pilot study that meets the federal definition of low risk.

### 5.1 Study Oversight:

The Study Chair has primary oversight responsibility of this clinical trial. The NIH appointed Data Safety Monitoring Board (DSMB) has oversight responsibility of the Data Safety Monitoring Plan (DSMP) for this clinical trial. The DSMB will review accrual, patterns and frequencies of all adverse events, and protocol compliance every 6 months. The D/OSMB makes recommendations to the NIH regarding the continuation status of the protocol.

Each site's Principal Investigator and their research team (co-Investigators, research nurses, clinical trial coordinators, and data managers) are responsible for identifying adverse events. Either the Principal Investigator or one of the co-Investigators will call each subject weekly during the study period to remind them to change the dose of medication, and to assess for any potential adverse events. All subjects will undergo a blood test for complete blood count and urine test for urinalysis within one month of completing the study to monitor for any adverse effects from the changes in medication dosages. The results of the blood and urine tests will be reviewed by the Principal Investigator. All adverse events will be reported to the DSMB. Aggregate report- detailed by severity, attribution (expected or unexpected), and relationship to the study drug/study procedures – will be available from the DMCC for site review. The research

team will then evaluate whether the protocol or informed consent document requires revision based on the reports.

## **5.2 Adverse Event Definitions and Standards:**

The Rare Diseases Clinical Research Network defines an adverse event as: “...an unfavorable and unintended sign, symptom or disease associated with a participant’s participation in a Rare Diseases Clinical Research Network study.”

Serious adverse events include those events that: “result in death; are life-threatening; require inpatient hospitalization or prolongation of existing hospitalization; create persistent or significant disability/incapacity, or a congenital anomaly/birth defects.”

An unexpected adverse event is defined as any adverse experience...the specificity or severity of which is not consistent with the risks of information described in the protocol.

Expected adverse events are those that are identified in the research protocol as having been previously associated with or having the potential to arise as a consequence of participation in the study.

All reported adverse events will be classified using the current version of the Common Terminology Criteria for Adverse Events (CTCAE) developed and maintained by CTEP at National Cancer Institute.

## **5.3 Expected/Known Risks/Discomforts/Adverse Events Associated with Study Intervention and Procedures: Definition of Expected Adverse Events:**

The period off Tiopronin is only a week. During that period, the patients will continue their alkali therapy, if prescribed, and their usual fluid intake and dietary restrictions. Therefore the week off Tiopronin is extremely unlikely to lead to cystine stone formation. That is particularly true since dosing of Tiopronin is completely empirical and not based on cystine supersaturation values; in other words, the doses have not been titrated to a particular level to achieve a particular therapeutic effect. In the previous study, no episodes of renal colic occurred during the week off Tiopronin.

Tiopronin is associated with allergy and other side effects, most of which are considered idiosyncratic and not clearly dose-related. Patients will take 0.5-2g, which is less likely to exceed their usual doses. The duration at each dose is a week. Since all patients are taking the drugs for inclusion, it is again very unlikely that patients will experience any important allergy or toxicity of the drugs in the short time they take doses different than their usual doses.

Patients will be closely monitored during the time in the study and will have frequent contact with the investigators in order to report any AEs in the course of the study. Patients will be contacted by phone at least weekly to be asked about any potential adverse effects.

## **5.4 Reporting Timeline:**

Within 24 hours (of learning of the event), investigators must report any reportable Serious Adverse Event (SAE) that:

- o Is considered life-threatening/disabling or results in death of subject-OR-
- o Is Unexpected/Unanticipated. Investigators must report all other reportable SAEs within 5 working days (of learning of the event).

All other (suspected) reportable AEs must be reported to the RDCRN within 20 working days of the notification of the event or of the site becoming aware of the event.

Local institutional reporting requirements to IRBs, any GCRC oversight committee and the FDA, if appropriate, remain the responsibility of the treating physician and the Study Chair.

### **5.5 RDCRN Adverse Event Data Management System (AEDAMS):**

Upon entry of a serious adverse event, the DMCC created Adverse Event Data Management System (AEDAMS) will immediately notify the Study Chair, site PIs, the Medical Review Officer, and any additional agencies (if applicable- industry sponsor, CTEP, etc) of any reported adverse events via email.

Serious adverse events: The NIH appointed Medical Review Officer (MRO) determines causality (definitely not related, probably not related, possibly related, probably related, definitely related) of the adverse event. The MRO may request further information if necessary and possibly request changes to the protocol or consent form as a consequence of the adverse event. A back-up notification system is in place so that any delays in review by the MRO beyond a specified period of time are forwarded to a secondary reviewer. The Adverse Event Data Management System (AEDAMS) maintains audit trails and stores data (and data updated) and communication related to any adverse event in the study.

Non-serious expected adverse events: Except those listed above as immediately reportable, non-serious expected adverse events that are reported to or observed by the investigator or a member of his/her research team will be submitted to the DMCC in a timely fashion (within 20 working days). The events will be presented in tabular form and given to the MRO and RDCRN DSMB on a bi-annual basis. Local site investigators are also required to fulfill all reporting requirements of their local institutions.

The DMCC will post aggregate reports of all reported adverse events for site investigators and IRBs.

### **5.6 Unanticipated Problem Reporting**

The Office for Human Research Protections (OHRP) considers unanticipated problems involving risks to subjects or others to include, in general, any incident, experience, or outcome that meets **all** of the following criteria:

- unexpected in terms of nature, severity, or frequency given (a) the research procedures that are described in the protocol-related documents, such as the IRB-approved research

protocol and informed consent document; and (b) the characteristics of the subject population being studied;

- related or possibly related to participation in the research (“possibly related” means there is a reasonable possibility that the incident, experience, or outcome may have been caused by the procedures involved in the research); and
- suggests that the research places subjects or others at a greater risk of harm (including physical, psychological, economic, or social harm) than was previously known or recognized.

Per the definition, only a subset of adverse events would be characterized as unanticipated problems. There are other types of incidents, experiences, and outcomes that are not considered adverse events, but are characterized as unanticipated problems (e.g., breach of confidentiality or other incidents involving social or economic harm).

Incidents or events that meet the OHRP criteria for unanticipated problems are to be reported to the IRB, per local institutional reporting requirements. Local institutional reporting requirements to IRBs, any GCRC oversight committee and the FDA, if appropriate, remain the responsibility of the treating physician and the Study Chair.

